### Study Design:

This is a Phase 2b/3, randomized, double-blind, placebo-controlled, dose-ranging study to investigate PF-06651600 in AA. The study will have a maximum duration of approximately 57 weeks. This includes an up to 5-week Screening period, a 48-week treatment period, and a 4-week follow-up period as shown below. The treatment period will be comprised of a placebo-controlled period that includes a 4-week loading phase and a 20-week maintenance phase, followed by a 24-week extension phase. The study will enroll a total of approximately 660 subjects. The study will be conducted at approximately 120 sites.

\* Primary endpoint is response based on absolute Severity of Alopecia Tool (SALT) Score  $\leq 20$  at Week 24.

To be eligible to enroll in this study, subjects must have moderate to severe AA with  $\geq 50\%$  hair loss of the scalp (Severity of Alopecia Tool [SALT] score  $\geq 50$ ) at both Screening and baseline visits, without evidence of terminal hair regrowth within the previous 6 months and with the current episode of hair loss  $\leq 10$  years.

Screening will occur within 35 days prior to the first dose of study drug to confirm that subjects meet selection criteria for the study. Eligible subjects will be randomized as described below.

A stratified randomization will be used for operational purposes in order to achieve a target global composition for AT/AU and adolescent subjects in the enrolled population. The targets for enrollment are approximately 40% AT/AU and approximately 15% adolescents. The randomization will be operationalized as follows. In regions enrolling both adolescents and adults, there will be four strata:

- <18 years of age and AT/AU;
- <18 years of age and not AT/AU;
- $\geq 18$  years of age and AT/AU; and
- $\geq 18$  years of age and not AT/AU.

Within each of these strata, subjects will be randomized in a 2:2:2:2:1:1:1 manner to blinded PF-06651600 and matching placebo for a total of 7 treatment sequences.

In regions enrolling only adults, there will be two strata:

≥18 years of age and AT/AU; and

≥18 years of age and not AT/AU.

In these regions, subjects will be randomized using the same ratio as described for regions enrolling both adolescents and adults.

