### 3. STUDY DESIGN

Study B7981015 will investigate PF-06651600 in subjects with moderate to severe AA. This is a Phase 2b/3, randomized, double-blind, placebo-controlled, dose-ranging study. The study will have a maximum duration of approximately 57 weeks. This includes an up to 5-week Screening period, a 48-week treatment period, and a 4-week follow-up period as shown in [Figure 1](#). The treatment period will be comprised of a placebo-controlled period that includes a 4-week loading phase and a 20-week maintenance phase, followed by a 24-week extension phase. The study will enroll a total of approximately 660 subjects. The study will be conducted at approximately 120 sites.

To be eligible to enroll in this study, subjects must have moderate to severe AA with  $\geq 50\%$  hair loss of the scalp (SALT score  $\geq 50$ ) at both Screening and baseline visits, without evidence of terminal hair regrowth within the previous 6 months and with the current episode of hair loss  $\leq 10$  years. The full list of eligibility criteria for the study is included in [Section 4](#).

Screening will occur within 35 days prior to the first dose of study drug to confirm that subjects meet selection criteria for the study. Photographs will be taken at the Screening Visit to verify eligibility (AA with  $\geq 50\%$  hair loss of the scalp). Eligible subjects will be randomized as described below.

A stratified randomization will be used for operational purposes in order to achieve a target global composition for AT/AU and adolescent subjects in the enrolled population. The targets for enrollment are approximately 40% AT/AU and approximately 15% adolescents.

The randomization will be operationalized as follows. In regions enrolling both adolescents and adults, there will be four strata:

- <18 years of age and AT/AU;
- <18 years of age and not AT/AU;
- ≥18 years of age and AT/AU; and
- ≥18 years of age and not AT/AU.

Within each of these strata, subjects will be randomized in a 2:2:2:2:1:1:1 manner to blinded PF-06651600 and matching placebo for a total of 7 treatment sequences.

[figure not shown]
In regions enrolling only adults, there will be two strata:

- ≥18 years of age and AT/AU; and
- ≥18 years of age and not AT/AU.

In these regions, subjects will be randomized using the same ratio as described for regions enrolling both adolescents and adults.

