  - A postmenopausal state is defined as no menses for 12 months without an alternative medical cause. In addition, a high follicle stimulating hormone (FSH) level in the postmenopausal range must be used to confirm a postmenopausal state in women under 60 years old and not using hormonal contraception or hormone replacement therapy (HRT). Females on HRT and whose menopausal status is in doubt will be required to use one of the nonestrogen hormonal highly effective contraception methods if they wish to continue their HRT during the study. Otherwise, they must discontinue HRT to allow confirmation of postmenopausal status before study enrollment.

The investigator is responsible for review of medical history, menstrual history, and recent sexual activity to decrease the risk for inclusion of a woman with an early undetected pregnancy. Documentation of this review should be included in the participant's medical record for the study.

Males:

Outside of VHP countries in the EMA, no contraceptive methods are required for male subjects in this study.

Within VHP countries in the EMA, male subjects are eligible to participate if they agree to the following requirements during the intervention period and for at least 90 days after the last dose of study intervention:

- Refrain from donating sperm.

AND

- Use one acceptable method of contraception as described in [Section 4.3](#).

5. Must meet the following AA criteria:

- a. Have a clinical diagnosis of AA with no other etiology of hair loss (eg, telogen effluvium, androgenetic alopecia, etc.).
- b.  $\geq 50\%$  hair loss of the scalp, including alopecia totalis (AT) and alopecia universalis (AU), without evidence of terminal hair regrowth within 6 months at both the screening and baseline visits.
  - AT is defined as complete (100%) scalp hair loss.
  - AU is defined as complete (100%) scalp, facial, and body hair loss.
  - Percentage of hair loss on the scalp will be measured by SALT.

- Photographs taken at Screening must be submitted to the Sponsor or designee for verification of SALT score  $\geq 50$  and hair loss due to AA. Subjects must not be randomized until verification has been confirmed.
- c. Current episode of hair loss  $\leq 10$  years.

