5.2.1. Binary Endpoints

Planned analysis for the overall study, for the FDA/PMDA and for the EMA and competent authorities in the VHP countries are summarized in Table 5.

Table 5. Statistical Methods of Planned Analysis for Primary and Key Secondary Endpoints for the Study and for each Regulatory Region

Study or Region	Endpoint/designation	Analysis #	Analysis Designation	Statistical Method	Missing due to COVID-19	Missing due to other reasons
Overall Study	SALT \leq 20 at Week 24/primary	Analysis 1	Primary	MN	Exclude	non-responders
		Analysis 2	Supplementary	GLMM	MAR	MAR
		Analysis 2a	Supplementary	GLMM/TP	MNAR	MNAR
		Analysis 3	Supplementary	MN	non-responders	non-responders
	SALT \leq 10 at Week 24/key secondary	Analysis 1	Key Secondary	MN	exclude	non-responders
		Analysis 3	Supplementary	MN	non-responders	non-responders
FDA/PMDA	SALT \leq 20 at Week 24/primary	Analysis 1	Primary	MN	exclude	non-responders
		Analysis 2	Supplementary	GLMM	MAR	MAR
		Analysis 2a	Supplementary	GLMM/TP	MNAR	MNAR
		Analysis 3	Supplementary	MN	non-responders	non-responders
EMA and competent authorities in VHP countries	SALT \leq 10 at Week 24/primary	Analysis 4	Primary	GLMM	MAR	non-responders
		Analysis 4a	Supplementary	GLMM/TP	MNAR	non-responders
		Analysis 1	Supplementary	MN	exclude	non-responders
		Analysis 3	Supplementary	MN	non-responders	non-responders
	PGI-C Response at Week 24/key secondary	Analysis 4	Key Secondary	GLMM	MAR	non-responders

Abbreviations: GLMM = Generalized linear mixed model; MN = Miettinen and Nurminen; MAR = Missing at random; MNAR = Missing not at random; TP = Tipping point

5.2.1.1. Miettinen and Nurminen – Analysis 1 and Analysis 3

The Miettinen and Nurminen (MN) method will be used to calculate 95% confidence intervals (CI) and p-values for the difference in the proportion of responders between each active treatment group and placebo. Subjects with missing SALT score at Week 24 due to COVID-19 related reasons will be excluded from the analysis at that time point, whereas subjects with missing SALT scores due to other reasons will be counted as non-responders at that time point (Analysis 1).

As a supplementary analysis to assess the impact of COVID-19-related missing data on the results of the primary analysis, a similar analysis will be conducted with all missing data considered as non-responders regardless of the reason for missingness (Analysis 3).

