5.2.1.2. Generalized Linear Mixed Model and Tipping Point – Analyses 2 and 2a

As a supplementary analysis, the primary endpoint for the overall study and for the FDA/PMDA will also be analyzed utilizing a generalized linear mixed model (GLMM) for longitudinal binary data of response based on $SALT \leq 20$ over time up to Week 24. This binary outcome will be modeled using a logistic-normal distribution. Fixed factors in this model are treatment (6 levels), visit (5 levels) and treatment-by-visit interaction. Visit will be modeled as a categorical covariate. A subject-specific random intercept will be used to model the correlation within a subject over time. Due to the expected negligible placebo response, a Bayesian estimation will be carried out in which diffusive priors will be used and the placebo response probability will be bounded away from 0 to avoid the potential convergence issues. From this model, one can derive the estimates of the marginal probability of response for each treatment group at each visit as well as inferential comparisons (the proportional difference between active and placebo groups, CIs and p-values) between treatment groups after the random effect is integrated out from the posterior samples. Given that this random intercept model specifies the full joint distribution for the outcome, the inference for the marginal proportions will be valid in the presence of missing data when the missing mechanism is missing at random (MAR). This inference will be with respect to the difference in treatments assuming all subjects maintained their randomized therapy. This analysis will be referred to as Analysis 2.

A tipping point analysis will be conducted under the assumption of missing not at random (MNAR). The imputations will be implemented under the framework of the same logit normal GLMM as above. Imputation of missing SALT response is performed only at Week 24 based on the predictive distribution of the GLMM. Under MNAR assumption, a fixed MNAR quantity (favorable or unfavorable), delta, will be applied to the probability of response at Week 24 for subjects with missing SALT response in the PF 06651600 dose groups and placebo group independently to assess when the conclusion might change (ie, tipping). Imputations will be repeated to obtain completed datasets. The Rubin's rules^{4,6} will be used to combine the results of multiple imputed samples for inference. This analysis will be referred to as Analysis 2a.

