5.2.1.3. Generalized Linear Mixed Model and Tipping Point – Analyses 4 and 4a

The primary analysis of the primary endpoint for the EMA and competent authorities in the VHP countries will be based on a MAR assumption and use multiple imputation methods similar to those described in [Section 5.2.1.2](#). In this analysis, while subjects with missing SALT scores due to COVID-19 will be assumed to be MAR, subjects with missing SALT scores due to other reasons will be treated as non-responders. This analysis will be referred to as Analysis 4.

A tipping point analysis will be conducted similar to that described in [Section 5.2.1.2](#). While the analysis for the study and for the FDA/PMDA will treat missing as MNAR regardless of the reason for missingness, the analysis for the EMA will treat missing due to COVID-19 as MNAR but missing due to other reasons will be considered as non-responders. This analysis will be referred to as Analysis 4a.

The key secondary endpoint, PGI-C response at Week 24, will also be analyzed using this approach.

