5.2.3. Continuous Endpoints

For continuous secondary endpoints up to Week 24, a mixed-effect model with repeated measures (MMRM) will be used. This model will include the factors (fixed effects) for treatment group, visit, treatment-by-visit interaction, and relevant baseline value when

modeling the change from baseline. Within the framework of MMRM, the treatment difference will be tested at each time point. Visit will be modeled as a categorical covariate. Unstructured covariance matrix will be assumed for the model errors.

When modeling the change from baseline values, the variable for visit will start with the first post-baseline visit, and the actual baseline value will be included as a covariate. At each visit, estimates of least square mean (LSM) values and the LSM differences between the PF-06651600-treated groups and the placebo group will be derived from the model. The corresponding p-values, standard errors and 95% CIs will also be derived from the model. Estimates of the difference in LSMs along with the two-sided 95% CI will also be provided for the treatment groups versus placebo group for the initial 24 weeks.

Exploratory endpoints will be summarized using descriptive statistics unless specified otherwise.

The MMRM method described above will also be applied to the continuous data up to Week 48 (over the entire study) for initial active treatment groups. LSM, standard error and 95% CI will be presented for each treatment group without treatment comparison. Descriptive statistics based on the observed case data will also be provided from baseline to Week 48 by 7 treatment sequences ([Figure 1](#)), without combining two placebo groups, as supportive.

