6.5. Subset Analyses

Summary statistics for SALT ≤ 20 at week 24, SALT ≤ 10 at week 24 and PGI-C response at Week 24 will be presented by subgroups as below:

- Age (years) at baseline (12-17, ≥ 18);
- Age (years) at baseline (12-17, 18-44, 45-64, ≥ 65);
- Body Mass Index (BMI) group at baseline (< 25 , 25-30, ≥ 30);
- Weight at baseline ($<$ median, \geq median);
- Gender (Male, Female);
- Race (White, Black, Asian, Other);
- Region of enrollment (North America, Europe, Asia, Rest of World) as specified in [Section 9.4](#);
- Baseline disease severity (AT/AU, non AT/AU);
- AA duration since first diagnosis (years) ($<$ median, \geq median);
 - The median of the entire sample will be used as the cut-off value.
- Duration of onset of current AA episode (years) ($<$ median, \geq median);
 - The median of the entire sample will be used as the cut-off value.
- Prior pharmacological treatment of AA (yes, no); [Section 9.7](#).

Estimates of the response rates for each dose compared to the placebo group and its 95% CI based on MN method, will be presented for each defined category of each subgroup. No p-values will be presented.

The primary purpose of the subgroup analyses is to check for consistency of results across subgroups. There is no intention to have any specific inference within subgroups. The analysis described in this SAP may be repeated on the specific country and/or region subpopulation sets in order to meet country-specific regulatory requirements.

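### The MN analyses ignore the AT/AU randomisation strata: valid and slightly conservative, with a small efficiency gain available from stratifying by AT/AU

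*SAP*

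**What the plan says.** Protocol section 3 and SAP 2.2 set four strata (AT/AU or not, under 18 or 18 and over) where adolescents are enrolled, and two AT/AU strata in adult-only regions: "Within each of these strata, subjects will be randomized in a 2:2:2:2:1:1:1 manner". The stated motive is enrolment mix: "A stratified randomization will be used for operational purposes in order to achieve a target global composition", with targets of about 40% AT/AU and 15% adolescents.

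The efficacy analyses do not use these strata:

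- **MN (Analyses 1 and 3), SAP 5.2.1.1:** "The Miettinen and Nurminen (MN) method will be used to calculate 95% confidence intervals (CI) and p-values for the difference in the proportion". Every active group is compared with placebo in this way. No stratification is mentioned there or in Protocol Table 6.
- **GLMM (Analyses 2 and 2a), SAP 5.2.1.2:** "Fixed factors in this model are treatment (6 levels), visit (5 levels) and treatment-by-visit interaction". Analysis 4, the EMA primary (SAP 5.2.1.3), "will be based on a MAR assumption and use multiple imputation methods similar to those described in" that section.
- **MMRM, SAP 5.2.3:** "This model will include the factors (fixed effects) for treatment group, visit, treatment-by-visit interaction, and relevant baseline value".

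AT/AU returns only as a subgroup in SAP 6.5, "Baseline disease severity (AT/AU, non AT/AU", with estimates and intervals but no p-values. Age group is handled the same way.

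**The concern.** Allocating within strata balances AT/AU between arms. If AT/AU also predicts response, an unstratified variance still counts variation that this balance has removed, so the standard error is somewhat too large.

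A prognostic effect is plausible. Protocol 4.1 states that "AT is defined as complete (100%) scalp hair loss", and AU also requires complete scalp loss, whereas other subjects may enter at SALT 50. AT/AU subjects therefore have further to go to reach SALT ≤20 or ≤10. Protocol 1.2.1 also describes the extensive forms as frequently resistant to treatment.

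What is at stake is power for the weaker regimens. H2 and H3 start at 0.05/4 = 0.0125 for the overall study, 0.01/4 = 0.0025 for the EMA and 0.00125/2 = 0.000625 for FDA/PMDA. H4 can be tested only if both succeed.

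**Working it through.** **Inputs from the documents.** There are 120 subjects per main active group. Placebo is F + G pooled, 660 × 2/11 = 120. The 200/50 mg assumptions are 29% vs 5% (SALT ≤20) and 25% vs 5% (SALT ≤10). AT/AU is 40%, or 48 of 120.

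**Assumptions.** r is the AT/AU response rate divided by the non-AT/AU rate, equal in both arms, at 0.67, 0.5, 0.33 and 0.2. Weaker regimens are set at 20% vs 5%. The documents give neither.

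**The plan's own figure.** Normal approximation, 29% vs 5%, two-sided 0.00125 (z = 3.227), pooled rate 17%:

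- null SE = √(2 × 0.1411/120) = 0.0485
- alternative SE = √((0.2059 + 0.0475)/120) = 0.0460
- (0.24 − 3.227 × 0.0485)/0.0460 ≈ 1.82, giving 96.5% power

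The same method gives 99.9% at 0.05, and 96.7% for 25% vs 5% at 0.01. The stated >90% holds without stratification.

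**Stratum rates.** Solve 0.4·r·x + 0.6·x = p for the non-AT/AU rate x.

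| r | 29%: AT/AU / not | 5%: AT/AU / not |
|---|---|---|
| 0.67 | 22.3 / 33.5 | 3.8 / 5.8 |
| 0.5 | 18.1 / 36.3 | 3.1 / 6.3 |
| 0.33 | 13.2 / 39.5 | 2.3 / 6.8 |
| 0.2 | 8.5 / 42.6 | 1.5 / 7.4 |

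**Excess standard error** = √(unstratified variance / within-stratum variance) − 1. Two variances matter. The unrestricted variance approximates interval width. The null-restricted variance is the one the MN test uses at difference 0.

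Worked case, r = 0.2, 29% vs 5%:

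- Interval: (0.2059 + 0.0475)/(0.1780 + 0.0467) = 1.128, root 1.062, so 6.2%.
- Test: pooled rates are 17% overall and 5.0% / 25.0% by stratum. Then 0.1411/(0.4 × 0.0475 + 0.6 × 0.1875) = 0.1411/0.1315 = 1.073, root 1.036, so 3.6%.

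| Rates | Excess SE for | r = 0.67 | 0.5 | 0.33 | 0.2 |
|---|---|---|---|---|---|
| 29% vs 5% | interval | 0.6% | 1.6% | 3.6% | 6.2% |
| 29% vs 5% | test | 0.4% | 1.0% | 2.1% | 3.6% |
| 20% vs 5% | interval | 0.4% | 1.0% | 2.1% | 3.6% |
| 20% vs 5% | test | 0.2% | 0.7% | 1.5% | 2.5% |

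**Power.** Simulation, 400,000 trials per case, 48/72 per group, no missing data. The unstratified MN score test is compared with MN stratified by AT/AU (CMH weights).

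Top dose, SALT ≤20 at 0.00125: 98.0% for both at r = 0.67; 98.3% to 98.7% at r = 0.2.

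Gain in points for 20% vs 5%:

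| Level | r = 1 | 0.67 | 0.5 | 0.33 | 0.2 |
|---|---|---|---|---|---|
| 0.0125 (overall) | 0.2 | 0.5 | 0.9 | 1.3 | 1.6 |
| 0.0025 (EMA) | 0.0 | 0.2 | 0.5 | 1.1 | 2.1 |
| 0.000625 (FDA/PMDA) | 0.2 | 0.6 | 1.3 | 2.6 | 4.0 |

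The largest gain, at 0.000625 and r = 0.2, is from 55.0% to 59.0%. The EMA row uses MN as a proxy, because the EMA primary analysis is the GLMM. The r = 1 column is a control: with no prognostic effect, a small gain remains because the stratified statistic is less discrete. If AT/AU counts are drawn binomially in each arm instead of fixed, the gains over r = 0.67 to 0.2 are 0.4–2.1, −0.2–2.6 and 0.3–3.7 points.

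**Type I error** at the planned 5% placebo rate, unstratified vs stratified: 4.4–4.6% vs 4.7–4.8% at 5%; about 1.0% for both at 1.25%; 0.04–0.05% vs 0.05–0.06% at 0.125%. All are below nominal.

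**The case against.** The strongest reply is that nothing is broken. The plan stratifies to control enrolment mix and says so. The estimate is unbiased, the test is valid, and at the only response rates the documents give the gain is at most 0.4 points. The larger gains need an assumed 20% response and a strong AT/AU effect. The JAK-inhibitor evidence in Protocol 1.2.1 ties non-response to AT/AU episodes lasting over 10 years, which the inclusion criteria exclude. AT/AU response rates with MN intervals are already prespecified as subgroups.

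Most of this stands. It makes the point optional and means r = 0.2 is an extreme, not an expectation. The r = 1 control also shows that part of the gain at mild r is not due to prognosis. The motive for stratifying does not settle the matter, though: allocation within strata balances AT/AU whatever the reason, and the unstratified variance does not credit that balance.

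A further objection is that a constant ratio implies unequal risk differences: at r = 0.2 and 29% vs 5%, about 7 points in AT/AU (8.5 − 1.5) and 35 in the rest (42.6 − 7.4). A stratified interval then describes a weighted average difference. Its coverage was not examined.

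**Conclusion.** The omission is real, and its consequence is small. Ignoring the strata makes MN slightly conservative if AT/AU is prognostic. For r from 0.67 to 0.2 at 29% vs 5%, the excess standard error is about 0.6–6.2% for interval width and 0.4–3.6% for the test. The power cost falls on the weaker regimens and is near nil if AT/AU is weakly prognostic. All by-stratum rates and the 20% rate are assumptions.

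A reader might infer more than this:

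- **That stratified randomisation without a stratified analysis biases the estimate, inflates type I error or undermines the stated power.** The calculations show none of these.
- **That the 6.2% figure applies to the hypothesis test.** It approximates interval width only.
- **That the GLMM and MMRM should also gain an AT/AU term.** Both omit the strata, but the effect there was not computed. The MMRM for change in SALT already adjusts for baseline SALT, which carries much of AT/AU. SAP 5.2.1.2 already anticipates convergence trouble from sparse placebo responses. No change to those models is proposed.

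**What to change.** Before unblinding, specify Analyses 1 and 3 as MN stratified by AT/AU only, with CMH weights, and keep unstratified MN as a sensitivity analysis. Collapse age in advance: adolescent AT/AU subjects number about 120 × 0.15 × 0.40 = 7 per 120-subject group (assuming age and AT/AU are independent), and Protocol 1.2.1 expects no difference in treatment response between adolescents and adults. Protocol section 9 requires a major change to a primary analysis to appear in a protocol amendment.

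Protocol 9.2.2 says the analyses were set out separately by region because of agency advice. If the primary analysis is to stay for that reason, add AT/AU-stratified MN as a prespecified sensitivity analysis instead.

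The cost is a few SAP lines and one extra table, plus the amendment if the primary analysis changes. No new data are needed, since AT/AU is known at randomisation. The SAP should say that the stratified interval summarises a weighted average difference if effects differ by stratum.
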